9. POTENTIAL RISKS

The behavioral and physiological assessment procedures employed in this study are benign. The risks to the study subjects are those related to the administration of the drugs under study. Cocaine has safely been administered to human subjects under controlled-laboratory conditions. The relative safety, as well as the contraindications and possible side effects of cocaine and zolmitriptan are well known and documented. However, the administration of any drug involves some risks simply because individuals differ in their reactions

to drugs. The main risk is that subjects will experience side effects that may be unpleasant. The side effects of zolmitriptan and cocaine may change as a function of the drug combinations, which is why we will not be dosing more than the recommended daily amount of zolmitriptan (i.e., 10 mg/day) in this study.

Common side effects of zolmitriptan include dry mouth, nausea, pain/pressure in neck or throat, drowsiness, weakness, warmth, redness or mild tingling under the skin, increased heart rate and increased blood pressure. More serious side effects include chest pain, sudden lateral numbness or weakness, sudden headache, confusion, problems with vision, speech or balance, dizziness, severe stomach pain, hematochezia, serotonin syndrome and cyanosis.

Common side effects of cocaine include anxiety, restlessness, diuresis, irritability, suppressed appetite, insomnia, gastrointestinal upset, increased heart rate, increased blood pressure, palpitations, and arrhythmias. More serious side effects following the chronic, unsupervised administration of much higher doses of cocaine have occurred and include psychotic episodes, suppressed breathing, seizures, myocardial infarctions, heart failure and death.

The doses to be administered in the present experiment were chosen to minimize, if not eliminate, the chance of these side effects occurring since these side effects are related to dose. Thus, it is unlikely that subjects will experience side effects during the experimental protocol. All experiments proposed in this application will be conducted at the CRU and under medical supervision. Side effects of the drugs are temporary, usually dissipating in less than 24 hours.

There is a theoretical risk that subjects might choose to seek out illicit sources of cocaine because of their exposure to the drug in this study. However, this risk is minimal because all drugs are administered under blind conditions and in a setting that is not conducive to the exacerbation of existing cocaine use disorder. Furthermore, all subjects will already have histories of cocaine use. Importantly, the consent document will list all drugs under study and subjects will be debriefed about the drugs under study following participation.

Cocaine will be administered intravenously through a midline catheter or peripheral catheter (if needed in lieu of the midline catheter) placed in each subject's non-dominant arm (if possible) and maintained per UK HealthCare policy. During catheter placement, there is some risk of bruising, soreness, infection, bleeding or blood clot, pain, irritation from the insertion of the needle, and malposition of the midline or peripheral catheters. However, these risks are minimal since standard sterile procedures will be used. There is also a risk of syncope. The likelihood of syncope is uncertain and will vary across subjects; however, all medical staff are prepared to manage the occurrence of syncope.

There is also the risk that a subject's protected health information (PHI) may be seen by others. PHI is considered individually identifiable health information transmitted or maintained in any form (electronic means, on paper, or through oral communication) that relates to the past, present or future physical or mental health or conditions of an individual that may be used or disclosed. The following PHI will be collected as part of this project: names (individual, employer, relatives, etc.), address, telephone number, Social Security number, dates (birth, admission, discharge), medical record numbers, driver's license numbers, mental and physical health history, drug use history, results from mental and physical health screening, results from personality questionnaires and data from experimental measures. This risk will be minimized since all appropriate precautions will be taken to protect subjects' PHI, according to the guidelines established by the HIPAA.

10. SAFETY PRECAUTIONS

Protocol management forms will include prompts for research staff members to record any protocol anomalies, data collection problems, concerns with study subjects, or any unusual events that could impact the safety of the subjects or the integrity of the protocol. In addition, the PI, as well as the study physician or his appointed representative, are always available by telephone to respond to any questions or concerns that occur during the study. Furthermore, the PI meets with the project staff on a regular basis in the laboratory or by telephone contact to review the study activities.

As described above, Drs. [name], [name], and [name] will screen all potential subjects for physical and psychiatric contraindications to participation. Urine samples will be monitored throughout each study to ensure that female subjects are not pregnant and that all subjects are adhering to the drug use restrictions. All subjects in these studies will be thoroughly informed of the various drug side-effects which they might experience and will be appropriately cautioned concerning their activities in the hours after drug administration. However, this should not pose a significant problem because research subjects will always be under the direct supervision of the nursing staff on the CRU during drug dosing. Participation is voluntary, so individuals can withdraw at any time if they find the behavioral procedures or drug effects undesirable. The drug doses to be administered in the present experiments were chosen to minimize, if not eliminate, the chance of these side effects occurring. As noted above, Drs. [name], [name], and [name] will screen all potential research subjects for medical contraindications, and [name] of the University of Kentucky Gill Heart & Vascular Institute will review the ECG, prior to study participation. Drs. [name], [name], and [name] will monitor research subjects throughout their participation. We anticipate that careful subject selection, dose selection and subject monitoring will greatly reduce, if not eliminate, the occurrence of serious side effects. The assembled team of investigators has been conducting inpatient and outpatient human behavioral pharmacology studies with healthy subjects and subjects with histories of drug abuse for more than 60 years combined and have never observed a serious drug-related unanticipated serious adverse event. To monitor for adverse events/side effects, the UKU Side Effects Rating Scale will be completed daily with subjects by CRU nursing staff. Staff observations, subjective-effects drug effects and spontaneous subject report will also be used to monitor for adverse events.

To minimize the risk associated with intravenous cocaine administration, dosing will occur under the supervision of ACLS-certified medical staff ([name] and CRU nurses). During the medical safety and experimental sessions, heart rate and blood pressure will be recorded 30 minutes prior to cocaine administration and at frequent intervals (i.e., 15 – 30 minutes) afterwards for the duration of the session. Electrocardiograms (ECG) will be recorded continuously during each experimental session. Electrocardiograms (ECG) will be recorded continuously during the medical safety and each experimental session. Cardiovascular hypersensitivity is defined as heart rate > 130 bpm, systolic pressure > 180 mmHg or diastolic pressure > 120 mmHg elevated consistently across a five-minute period of monitoring. Cardiovascular hypersensitivity also includes prolonged abnormal heart rhythmicity, which is defined as ventricular arrhythmias that occur at a frequency greater than 5 per minute, are multifocal, or occur as couplets (2 consecutive beats) or salvos (3 or more consecutive beats) and persist for greater than 15 min. Subjects that exhibit hypersensitivity (i.e., heart rate >130 bpm, systolic pressure > 180 mmHg, diastolic pressure > 120 mmHg, or clinically significant ECG changes) to the cardiovascular effects of cocaine and/or zolmitriptan at any point during this study will be excluded immediately from further research participation and will be followed until symptom resolution. In our previous studies with cocaine over the last 20 years, only two subjects have been excluded based on these criteria. Drs. [name], [name], [name], [name], [name] and [name] will train all staff on this project. No drugs (i.e., cocaine or zolmitriptan) will be administered if a subject's heart rate is \geq 90 bpm if systolic pressure \geq 140 or diastolic pressure \geq 90 mmHg. Heart rhythmicity will be recorded continuously via 3-lead telemetry during each experimental session and will be monitored continuously for a minimum of 15 minutes following each infusion. Ischemia or other abnormalities as described in the exclusion criteria would also be cause for discharge. A cardiovascular emergency will be managed using UK medical center procedures (i.e., response from a code blue team).

Subjects will be required to report a recent history of cocaine use via the smoked or intravenous route to be eligible for study participation. Therefore, subjects who do not have a history of intravenous cocaine use (i.e., those individuals reporting smoked cocaine) will likely be enrolled and receive cocaine by a new route of administration. The National Advisory Council on Drug Abuse guidelines indicate that "a thorough assessment of the risks entailed if participants are to be exposed to a new route of administration than they would normally encounter by their own choice in their usual circumstance." We do not feel that the administration of intravenous cocaine to subjects who report no previous experience by this route of administration puts subjects at undue risk for two reasons. First, smoked cocaine administration results in a rapid onset and greater self-

reported effects compared to intravenous cocaine at doses that produce comparable blood concentrations, and smoked cocaine was chosen over intravenous cocaine in a self-administration procedure, suggesting that the abuse potential of intravenous cocaine is less than smoked cocaine (Cone, 1995; Foltin and Fischman, 1991, 1992). Second, a study that evaluated cocaine use patterns following investigational intravenous cocaine administration to intravenous-naïve cocaine users did not detect changes in frequency of illicit cocaine use or the adoption of intravenous use after study participation (Kaufman et al. 2000). Several investigative teams have published studies in which intravenous cocaine was administered to human subjects with a history of smoked, but not intravenous, cocaine (e.g., Haney et al., 1998; Newton et al., 2001; Walsh et al., 2010), demonstrating that the field finds this practice acceptable from an ethical standpoint. Also, worth noting is that some subjects who have participated in our previous research have reported intravenous cocaine use.

As noted above, serious side effects of stimulants include seizures. The occurrence of seizures appears to be related to the presence of certain predisposing factors including histories of head trauma, seizures or CNS tumors and the administration of concomitant medications that lower seizure threshold. Subjects that report personal histories of head trauma, seizures or CNS tumors or a first-degree family history of seizures will be excluded from research participation. Most seizures resolve of their own accord and typically, individuals with a history of seizures will be the only ones who require intervention. If a seizure should occur, we will follow the expert guidance/protocol of the UK Department of Neurology Rapid Response Team for seizure management, and [name] therapy preference, which consists of the following:

1. Assess and support respiratory and cardiac status.
2. If seizure is sustained for > 5 min, give immediate therapy with IV lorazepam (0.1 mg/kg/dose; max 4 mg/dose).
3. Repeat therapy every 5 min as need for continued/repeat seizures.

A physician in Neurology will be consulted if a second treatment dose is required. If the seizure has not stopped within the allotted time, diazepam is to be administered by the attending physician or their designee. Because we exclude individuals with a history or risk of seizures, it is very unlikely that a subject will have a seizure or that we will need to administer diazepam. If a research subject experiences a seizure, he/she will be excluded from further research participation.

Potential subjects must meet criteria for cocaine use disorder to be enrolled in the proposed experiments. It is possible that these subjects will experience abstinence symptoms once admitted to the CRU. As noted above, we have several safeguards in place to monitor for adverse events. If a subject experiences significant abstinence symptoms following admission to the CRU, he or she will be treated in accordance with the standard practice of the University of Kentucky Hospital and then dismissed from the study.

To avoid potential drug interactions, volunteers taking any prescribed medication chronically, except birth control, will be excluded. The medical personnel on this protocol will determine if it is safe for a potential volunteer to discontinue taking their medication during their participation.

During participation in the research, a subject could experience dissatisfaction or discomfort with the experimental procedures. A research staff member will be immediately available to address these issues, and the study subjects have telephone contact information to reach both the PI and the study physician. In addition, if individuals become overly distressed or distraught, participation in the study is discontinued immediately and private consultation with the study physician and/or PI is offered immediately.

Legal risks including loss of confidentiality: All subject PHI is confidential and will be protected according to the guidelines established by the HIPAA. An "Authorization to use and disclose PHI for research purposes" approved by the UK IRB will be obtained. This allows the investigators on this project to use or share health information with the United States Department of Health and Human Services (DHHS) representatives, the UK IRB, the UK Office of Research Integrity (ORI), UK medical center representatives, other research collaborators or when required by law. In addition, this project qualifies for a Certificate of Confidentiality from NIDA. All PHI will be protected as described above for safeguarding experimental data and PHI in the Research Materials section.

11. BENEFIT vs. RISK

The degree of risk to which individual study subjects are exposed because of their research participation is slight. In contrast, the potential and probable benefits to be derived by society in general and by patients as a group appear to be considerable. The major benefits of these studies are clinical and scientific ones related to the knowledge gained about putative neurobiological mechanisms underlying and medications for cocaine use disorder. The data from this project will contribute to a better understanding of substance use disorder and will ultimately contribute to the development of improved prevention, control, and treatment procedures. Individual study subjects are expected to benefit personally from the financial payments that are provided for their research participation, from the medical and psychiatric evaluations and from referrals for medical and psychiatric treatment that are provided whenever appropriate. Overall, the risk/benefit ratio appears favorable, and the conduct of this research seems well justified.

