2. Persistent hypertension $\geq 140/80$ mmHg or tachycardia (i.e., over 100 bpm) during screening will be excluded during screening (i.e., two or more screening visits).
3. Electrocardiogram abnormalities, including:
 - Atrial premature beats (≥ 2 consecutive)
 - Ventricular premature beats (Lown's Grade 3 or higher; ≥ 2 consecutive beats, multifocal)
 - Heartblock (2nd or 3rd degree AV block or bundle branch block)
 - Pre-excitation syndromes (Wolff-Parkinson-White or Lown-Ganong-Levine)
4. History of serious physical disease, current physical disease, impaired cardiovascular functioning, chronic obstructive pulmonary disease, history of seizure, chest pain, loss of consciousness, seizure, and/or paranoid episode following cocaine use, head trauma, phenylketonuria, or current or past histories

of serious psychiatric disorder and suicidal risk that in the opinion of the study physician would interfere with study participation.

5. Subjects who report a positive first-degree family history of cardiovascular disease or seizure disorders will also be excluded from research participation.
6. Potential subjects that meet moderate-severe diagnostic criteria for any other substance use disorder, other than tobacco use disorder, at the time of screening will not be eligible for study participation. Subjects who are physically dependent on a drug requiring medical detoxification (e.g., alcohol, opioids, benzodiazepines) will also not be eligible for the study. Urine drug screen must be negative for these drugs on admission to the inpatient unit.
7. Subjects with phenylketonuria, who are taking monoamine uptake inhibitors (including SSRIs), monoamine oxidase inhibitors, or cimetidine will not be eligible to participate.

Screening procedures for all subjects will include a medical history questionnaire, laboratory chemistries (blood chemistry screen, complete blood count, ECG, and urinalysis) and a brief psychiatric examination. These procedures will be conducted under our lab's screening protocol (#44379). All study participants will be judged by the study physicians, Drs. [name], [name], [name], or their representative, to be healthy.

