During the initial screening process, potential subjects will be asked to provide a urine specimen that will be screened for the presence of amphetamine, benzodiazepines, barbiturates, cocaine, methamphetamine, tetrahydrocannabinol (THC), and opioids. To participate in an experimental session, subjects must provide a urine negative for barbiturates, benzodiazepines, and opioids on each day of their participation. Subjects will be allowed to continue if they test positive for cocaine, if it is determined that this drug was given in a recent session, and it is likely that the result is positive due to experimental administration. [name], [name], or [name] will be notified of cocaine-positive urines on experimental session days and sessions will only proceed if subjects pass the sobriety test and have vital signs within acceptable limits (see below). Subjects will be maintained on a caffeine-free diet and will have to abstain from alcohol for the duration of their participation.

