Potential subjects will provide information regarding their drug use history and undergo an extensive physical and psychiatric health screening to determine their eligibility and safety of their participation. Potential subjects must meet DSM-5 criteria for cocaine use disorder and must present with a urine sample positive for cocaine at the time of screening. Any potential subject with a history of clinically significant physical disease, current physical disease (e.g., impaired cardiovascular functioning, histories of seizure, asthma, diabetes, head trauma or CNS tumors) or current or past histories of psychiatric disorder, other than substance abuse or dependence, will be excluded from research participation. Females must be using an effective form of birth control to participate and must not be pregnant. Methods for monitoring adverse events (AEs) will include observations by the medical and research staff, spontaneous report by the subjects, regular measurement of physiological indices and use of the UKU Side Effects Rating Scale and subjective measures. Subjects will not receive study drug if they have any signs or symptoms that may contraindicate its administration (e.g., heart rate and blood pressure outside of predetermined range for a prolonged period, development of serious side effects).

All AEs occurring during the study will be collected, documented, and reported to the PI. The occurrence of AEs will be assessed for the duration of participation and during the follow-up visit at 1-month following study completion. Each week a study investigator will review the AE forms from the previous week for events that were reported as new or continuing. The study investigators will follow all AEs to the point of a satisfactory resolution. Subjects may be withdrawn from the study if the medically responsible investigator determines it is the best decision to protect the safety of the subject. All AEs will be assessed to determine if they meet criteria for a serious adverse event (SAE).

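### The numeric pre-dose hold rule, read grammatically, withholds drug only when heart rate and blood pressure are both high, so high blood pressure alone does not trigger it

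*Combined protocol and SAP*

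**What the plan says.** **Hold rule.** Section 10 (Safety Precautions) states: "No drugs (i.e., cocaine or zolmitriptan) will be administered if a subject's heart rate is" 90 bpm or more, and continues with "90 bpm if systolic pressure" at or above 140 mmHg or diastolic at or above 90 mmHg. No word such as *and* or *or* joins heart rate to blood pressure; there is only a second *if*. Section 7 (Cardiovascular Measures and Body Temperature) has the same construction.

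**Related limits.** At screening, Section 4 joins the two quantities with *or*: persistent blood pressure of 140/80 or above "or tachycardia (i.e., over 100 bpm) during screening will be excluded during screening (i.e., two or more screening visits"). Section 4 also says that after a cocaine-positive urine on a session day, "sessions will only proceed if subjects pass the sobriety test and have vital signs within acceptable limits (see below"). Section 17 (Safety Monitoring Plan) bars study drug when any sign or symptom may contraindicate it, and gives as an example "heart rate and blood pressure outside of predetermined range for a prolonged period".

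**Exclusion rule.** Section 7 excludes a subject who at any time exceeds 130 bpm, 180 mmHg systolic or 120 mmHg diastolic. Section 10 defines cardiovascular hypersensitivity by the same cut-offs, "elevated consistently across a five-minute period of monitoring". It later excludes at once "Subjects that exhibit hypersensitivity (i.e., heart rate >130 bpm, systolic pressure > 180 mmHg, diastolic pressure > 120 mmHg", and so on, without repeating the duration. Heart rate and blood pressure are recorded before cocaine and "at frequent intervals (i.e., 15 – 30 minutes) afterwards for the duration of the session".

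**The concern.** The hold rule is the numeric check before each dose, and in a session infusions can follow one another at 60-minute intervals (Section 7, Table 2). Section 9 lists raised heart rate and raised blood pressure as common effects of both drugs, and says side effects may change with the combination. The medical safety session on Day 1 comes before any zolmitriptan, so it cannot reveal a response to the combination. If the rule needs both signs together, a subject with clearly raised blood pressure and an unremarkable heart rate passes it. The decision then rests on judgement, where the protocol meant to set a number.

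The exclusion wording raises a smaller question: does one brief exceedance end participation, or must it last five minutes?

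**Working it through.** No sample size or power figure is involved. The check applies the rules as written to example readings.

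**Inputs.** Hold limits: heart rate (HR) 90, systolic (SBP) 140, diastolic (DBP) 90 (Sections 7 and 10). Exclusion cut-offs: above 130, 180 and 120 (same sections). Screening heart-rate limit: over 100 (Section 4). Reading interval: 15 to 30 minutes (Section 10).

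**Rules compared.**
- L, the grammatical reading: HR ≥ 90 AND (SBP ≥ 140 OR DBP ≥ 90)
- O90: HR ≥ 90 OR SBP ≥ 140 OR DBP ≥ 90
- O100: HR > 100 OR SBP ≥ 140 OR DBP ≥ 90
- E, exclusion: HR > 130 OR SBP > 180 OR DBP > 120

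| HR, BP | L | O90 | O100 | E |
|---|---|---|---|---|
| 85, 175/115 | dose | hold | hold | not met |
| 89, 180/120 | dose | hold | hold | not met |
| 85, 150/85 | dose | hold | hold | not met |
| 125, 135/85 | dose | hold | hold | not met |
| 95, 120/75 | dose | hold | dose | not met |
| 95, 150/85 | hold | hold | hold | not met |

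First row: 85 ≥ 90 is false, so L is false whatever the blood pressure. For E, 85 ≤ 130, 175 ≤ 180 and 115 ≤ 120, so it is not met. In general, while heart rate is below 90, no blood pressure up to and including 180/120 triggers either numeric rule. The fourth row shows the mirror case: a heart rate of 125 with normal blood pressure also passes L. In the third row, 150/85 would exclude the subject if it persisted over two or more screening visits.

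**How often the rule is applied.** Per completer, 12 sessions × (1 sample + up to 5 choices) = 72 infusions, plus 3 in the medical safety session = up to 75. Of these, 8 non-zero sessions × 6 + 2 = up to 50 contain cocaine. In Table 1's illustrative schedule, capsules are given on days 2 to 31: 30 × 2 = 60 times, of which 18 days × 2 = 36 contain zolmitriptan. These are occasions on which the rule applies, not a count of doses given at high blood pressure.

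**Exclusion duration.** The most scheduled readings that can fall in a closed five-minute window is floor(5/15) + 1 = 1 at 15-minute spacing and floor(5/30) + 1 = 1 at 30-minute spacing. One SBP of 185 that settles within five minutes exceeds Section 7's cut-off but does not meet Section 10's definition. Continuous telemetry can show sustained heart rate; blood pressure has no equivalent in the text.

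**The case against.** The best defence is that the wording is a slip, a three-way *or* was intended, and experienced staff would apply it that way. Section 17 bars dosing on any contraindicating sign, and its vital-sign text is only an example, so 175/115 could fall under it. Section 4's reference to limits given below plausibly points to the hold rule. Dosing takes place under ACLS-certified supervision with a physician reachable.

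Much of this stands. A reader might infer that the protocol permits cocaine at 175/115. It does not go that far: Section 17 can still stop the dose. But Section 17 gives neither a range nor a period, and Section 4's reference leads back to the faulty sentence. No clear numeric rule stops the dose.

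The screening comparison is also imperfect. Screening concerns persistent elevation and uses a diastolic limit of 80, while the hold concerns a single pre-dose value and uses 90. It shows that the authors elsewhere treat either sign as enough; it does not prove what the hold should be.

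On exclusion, a reader might infer that Section 10 contradicts itself. Its second statement can be shorthand for the term it has just defined, and the medical safety session text in Section 7 only refers to limits set elsewhere. The conflict that remains is between Section 7's cardiovascular paragraph and Section 10. Nor do the documents make a five-minute elevation impossible to show: unscheduled repeat readings are not ruled out, and Section 7 says staff monitor subjects continuously. The repeat reading is simply not required.

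**Conclusion.** The hold rule is miswritten and should be corrected. On its grammatical reading it needs both signs, and it leaves systolic 140 to 180 and diastolic 90 to 120 outside every numeric rule while heart rate is below 90. The same construction appears in two sections, so a text-extraction error is unlikely. The conclusion rests on that reading; how staff apply the rule in practice is not documented.

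The exclusion mismatch is minor. The cut-offs agree, Section 7 is the stricter version, and Section 10 reports only two exclusions on these criteria in 20 years of cocaine studies. That history concerns exclusions and says nothing about how often a pre-dose hold would arise.

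A reader might also infer that withheld or wrongly given doses bias the break points. The documents give no frequency of holds, so they do not support that. This is a defect in a safety rule, not in the analysis.

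**What to change.** **Hold rule.** In Sections 7 and 10, state that neither cocaine nor zolmitriptan is given if systolic pressure is 140 mmHg or more, or diastolic is 90 mmHg or more, or heart rate reaches a limit confirmed by the study physicians. That limit could be 90 bpm or more, or over 100 bpm to match screening. The blood pressure part is the same either way.

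**Cost.** One sentence in two places. The downside depends on the heart-rate limit: screening admits subjects with resting rates of 90 to 100, and a hold on heart rate alone at 90 would withhold some of their doses. If 1%, 5% or 10% of infusion checks showed a rate of 90 to 100 with normal blood pressure (assumed; the documents give no figure), then 75 × 0.01 = 0.75, 75 × 0.05 = 3.75 or 75 × 0.10 = 7.5 infusions per completer would be withheld. A limit of over 100 avoids this.

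**Exclusion rule (minor).** Use one definition in Sections 7 and 10. If the five-minute definition is kept, require repeat blood pressure readings over five minutes after any exceedance. This costs a few readings, and only when a cut-off is exceeded. Neither change needs more subjects or sessions.
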